8.3	Anticipated Adverse Events	Error! Bookmark not defined.
8.4	Adverse Event Documentation.....	25
9	STATISTICAL CONSIDERATIONS.....	26
9.1	Sample Size	26
9.2	Descriptive Statistics.....	27
9.3	Handling of Missing Data	27
9.4	Demographics and Baseline Characteristics	27
9.5	Analysis of Study Outcomes	27
	9.5.1 Primary Outcomes.....	27
	9.5.2 Secondary Outcomes.....	28
	9.5.3 Objective Outcomes	28
10	ETHICS/PROTECTION OF HUMAN SUBJECTS.....	28
10.1	Ethical Standards and Guidelines	28
10.2	Institutional Review Board/ Ethics Committee	28
10.3	Informed Consent Process	29
10.4	Subject Confidentiality	29
11	DATA HANDLING AND RECORD KEEPING	30
11.1	Data Management Responsibilities	30
11.2	Data Capture Methods.....	30
11.3	Study Records Retention	30
11.4	Protocol Deviations.....	31
11.5	Amendments to the Protocol.....	31
12	STUDY CLOSE OUT	31
13	PUBLICATION/DATA SHARING POLICY	31
14	BIBLIOGRAPHY.....	32
	SUPPLEMENTAL MATERIALS	33
	APPENDICES.....	33

PROTOCOL SUMMARY

Title:	A Randomized, Post-market Study Evaluating Dermal Allograft Augmentation of Large and Massive Rotator Cuff Tears
Summary:	The purpose of this study is to compare postoperative healing of large and massive rotator cuff tears with preoperative MRI confirmed fatty infiltration stage II and higher repaired with or without dermal allograft augmentation (DAA).
Objectives and Outcome Measures:	
The primary objective is to evaluate postoperative healing of rotator cuff repair with and without DAA.
 
Primary: The primary outcome measure is healing evaluation in MRI
 
• MRI Post-Operative Assessment (Goutallier Stage and Sugaya Classification) 
Secondary: The secondary outcome measures are patient-reported outcome measures from validated outcome scoring systems, including:
 
• American Shoulder and Elbow Surgeons Score (ASES)• Single Assessment Numeric Evaluation score (SANE)• Visual Analog Scale (VAS) for pain• Veterans RAND Health Survey (VR-12)
Population:	Males and females between the ages of 30 and 75 years that require surgery for large and massive rotator cuff tears
Phase:	Post market
Description of Treatment:	Rotator cuff repair with or without augmentation using decellularized human dermal allograft.

Inclusion and Exclusion Criteria

Inclusion criteria:

1. The subject is between the ages of 30 and 75 years.
2. Subject is planning to undergo arthroscopic surgery for full-thickness rotator cuff tear (RCT)
3. Two complete RCTs or tear size equal to or greater than 3 cm in either the anterior-posterior or medial-lateral dimension
4. Primary rotator cuff repair
5. Stage II fatty infiltration or higher of the supraspinatus or infraspinatus muscle based on preoperative MRI6. Subject has a dual x-ray absorptiometry (DXA) or anterior posterior x-ray view of the target shoulder

Exclusion criteria:

1. The Subject is unable or unwilling to sign the patient informed consent, approved by the Institutional Review Board.
2. The subject objects to the use of allograft
3. Stage I or lower fatty infiltration of the supraspinatus AND infraspinatus muscle
4. Complete full-thickness subscapularis tears of greater than the superior one third of the tendon (Lafosse grade 3 and above)
5. Less than 2 mm joint space of the glenohumeral joint on either an anteroposterior or axillary radiograph
6. Recurrent shoulder instability
7. Corticosteroid injection in the operative shoulder within one month of surgery
8. Revision rotator cuff repair
9. Subject preoperative MRI obtained more than 12 months prior to surgery
10. Pregnant or planning to become pregnant during the study period
11. Workman's compensation case
12. Subject has conditions or circumstances that would interfere with study requirements.

[figure not shown]
Intraoperative exclusion criteria:

1. Partial rotator cuff repairs
2. Lafosse grade 3 or higher subscapularis tears

**Study Duration and
Subject
Participation:**

The enrollment period is estimated to be 12 months, with estimated subject participation of two years for a total study duration of approximately three years.

Schematic of Study Design:

2 BACKGROUND AND DEVICE DESCRIPTION

2.1 Background Information

Increasing tear size, increasing retraction, and fatty infiltration are the primary factors associated with decreased rates of tendon healing.^{1,2} The retear rate, for example, increases by 4-fold when tear size increases from 1 to 3 cm.² It is well-established that the most common mode of failure in large and massive rotator cuff tears, especially those with fatty degeneration infiltration, is tendon tearing through suture.³ Given the association between tendon healing and functional outcome⁴, it is important to identify techniques that can improve tendon healing.^{5,6,7}

Dermal allograft augmentation (DAA) has been shown to improve the biomechanics of rotator cuff repair, and case reports have described the capability for vascularization and neotendon formation.^{8,9} One study of 42 patients suggested that DAA can improve healing. However, repairs were limited to single-row constructs, which may have lower healing than double-row constructs.

2.2 Device(s) Description

Providing an efficient, simple approach to augmenting partial- and full-thickness rotator cuff tears, the CuffMend™ augmentation technique incorporates 1mm-thick ArthroFLEX® human dermal allograft for mechanical strength and to support healing. The graft is inserted with a graft spreader and securely fixed to native tendon using FiberStitch™ RC tendon anchors for medial soft-tissue fixation and Knotless PushLock® anchors for lateral bony fixation. The primary anchors utilized will be 3.5 mm PushLock® anchors (Arthrex Inc.). If poor bone quality is encountered the surgeon may use a larger anchor if required (i.e., 4.75 or 5.5 SwiveLock®; Arthrex, Inc) and the patient will not be excluded from analysis.

Scientific literature has shown acellular dermal allografts to be a safe and effective solution for rotator cuff repair augmentation.^{3,4}

Surgeons are advised to review the product-specific surgical technique prior to performing any surgery.

The devices are approved for marketing and will not be traced as required for pre-market devices. The standard traceability for all post-market medical device sales, shipments, and returns will be applied to the devices of this study.

Materials of the device(s) that come into contact with human tissue and body fluids have previously been described in United States (U.S.) marketing submissions and remain unchanged.

3 STUDY DESIGN

3.1 Study Design and Rationale

This is a prospective randomized study comparing the outcomes of patients undergoing rotator cuff repair with dermal allograft augmentation (DAA) or a control group without dermal allograft. Patient outcomes will be collected and compared between the two cohorts at two years postoperative and will include a range of subjective and functional outcomes and radiographic imaging. All patients undergoing primary rotator cuff repair surgery will be invited to be part of the study after pre-operative inclusion/exclusion criteria have been met.

Hypothesis: Patients undergoing rotator cuff repair surgery will experience improved tendon healing with the use of CuffMend™ dermal allograft augmentation.

The purpose of this study is to compare postoperative healing of large and massive rotator cuff tears with preoperative MRI confirmed fatty infiltration stage II and higher repaired with or without dermal allograft augmentation (DAA).

The outcome measures were selected based on the recommendations of the American Academy of Orthopaedic Surgeons (AAOS) and literature review.

3.2 Potential Risks and Benefits

3.2.1 Potential Risks

Potential risks from the surgery are equivalent to standard surgery and will be discussed with the patient as standard of care.

Potential risks related to the DAA include possible allergic or host reaction to the allograft. However, these risks are minimal.

Treatment risks are standard procedure risks that are discussed as part of orthopedic care. These include:

- Infections, both deep and superficial
- Allergies or other reactions to device materials
- Temporary or permanent nerve damage as a result of pressure or hematoma.
- Loosening of the implant or tissue reaction to implant
- Dislocation, subluxation, or inadequate scope of movement as a result of failure to achieve optimum positioning of the implant.
- Bone fractures as a result of one-sided overload or weakened bone structure.
- Allergic reaction to allograft or residual allograft processing reagents

3.2.2 Potential Benefits

The treatment may be obtained outside of the study and is considered standard of care. The benefit of participation in the study is furthering scientific knowledge of available treatments. There may not be a direct benefit to participation in this study. Future patients undergoing an RCR using DAA may benefit from the knowledge gained from this research.

3.3 Study Objectives and Outcome Measures

3.3.1 Study Objectives

The purpose of this study is to compare postoperative healing of large and massive rotator cuff tears with preoperative fatty infiltration stage II and higher repaired with or without DAA.

Primary Hypothesis: Improved postoperative healing with the addition of CuffMend™ DAA, assessed with MRI Imaging

Secondary Hypothesis: Improved Patient-Reported Outcomes and range of motion with the addition of CuffMend™ DAA

3.4 Study Outcome Measures

The primary outcome measure is the healing rate in MRI.

- MRI Post-Operative Assessment (Goutallier Stage and Sugaya Classification)

The secondary outcomes measures patient-reported outcomes from validated outcome scoring systems and range of motion objective measures.

- American Shoulder and Elbow Surgeons Score (ASES)
- Single Assessment Numeric Evaluation score (SANE)
- Visual Analog Scale (VAS) for pain
- Veterans RAND Health Survey (VR-12)
- ASES Objective Shoulder Assessment (ROM)

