3.6 Objective Outcome Measures

Shoulder range of motion (ROM) in forward flexion, external rotation at the side, external rotation at 90° of abduction, and internal rotation at 90° of abduction will be measured with a goniometer. Internal rotation will also be estimated to the nearest spinal level. The lead investigator or assigned research staff at each site will perform all measurements.

The MRI imaging will be collected according to standard of care pre-operatively and then at the 26 ± 8 weeks timepoint.

A standard shoulder MRI protocol utilizing a minimum of a 1.5 Tesla magnet shall be utilized. A recommendation for setting is: 5 pulse sequences, sagittal oblique T1-weighted and fast spin echo (FSE) T2-weighted with fat saturation, axial FSE proton density and FSE T2-weighted with fat saturation, and coronal oblique FSE T2-weighted with fat saturation. Post-operative cuff integrity will be classified utilizing the 5 categories described by Sugaya et al¹⁰: type I, sufficient thickness with homogenously low intensity; type II, sufficient thickness with partial high intensity; type III, insufficient thickness without discontinuity; type IV, presence of a minor discontinuity; type V, presence of a major discontinuity.

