6 STUDY SCHEDULE

Study Activity		Time Points						
		Pre-op/Baseline	Surgery	Two week post op (\pm 7 days)	6 weeks post op (\pm 7 days)	26 weeks (\pm 7 days)	1 Year (- 8 weeks + 12 weeks)	2 Year (-8 weeks + 12 weeks)
Signed Consent Form		X						
Review of Medical History Demographics/Diagnosis		X						
Inclusion/Exclusion Criteria form		X	X					
Randomization form			X					
Surgical details form			X					
Clinical Assessments	MRI	SOC				X		
	Rotator Cuff Assessment and Healing Index	X				X		
	Radiograph AP View or Bone Mineral Density Scan	SOC						
	ASES Range of Motion	X				X	X	
Patient Surveys	ASES	X				X	X	X
	VAS	X		X	X	X	X	X
	VR-12	X				X	X	X
	SANE	X				X	X	X
WHOOOP Management*		X**		X	X	X		
Assessment of Adverse Events			As occurs					

* for selected sites only

**Whoop set up and patient instruction for use

Diagnosis and intra-operative data will be obtained and will include but not be limited to the type and size of the rotator cuff tear.

Shoulder range of motion (ROM) in forward flexion, external rotation at the side, external rotation at 90° of abduction, and internal rotation at 90° of abduction will be measured with a goniometer. Internal rotation will also be estimated to the nearest spinal level. The lead investigator or assigned research staff at each site will perform all measurements.

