9.1 Sample Size

Sample size calculations were based on a one-sided Z-test for two proportions. The study was powered to detect a difference in the proportion healed in the treatment and control groups. The healing rate on the postoperative MRI in the treatment group was assumed to be 75%, and in the control group, 40%. Further assumptions included a one-sided alpha level of 0.025 and 90% power. Under these assumptions, 40 subjects per group are required. To account for a potential dropout of up to 33%, this study will enroll 120 total subjects (60 per group).

Sample size was estimated using PASS 2021 Power Analysis and Sample Size Software (2021). NCSS, LLC. Kaysville, Utah, USA, ncss.com/software/pass.

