9.5 Analysis of Study Outcomes

9.5.1 Primary Outcomes

The primary outcome of difference in healing rates between groups will be assessed under the following hypothesis:

$$H_0: \pi_T - \pi_C \leq 0$$

$$H_a: \pi_T - \pi_C > 0$$

Where π_T is the healing rate at six months in the treatment group (RCR + DAA) and π_C is healing rate in the control group (non-augmented RCR) at six months. The difference in rates between groups will be summarized, along with a 95% confidence interval.

A chi-square test will be performed to obtain a p-value of the comparisons between groups. A one-sided p-value of <0.025 will be used to define success of the hypothesis (i.e., postoperative healing is improved with the addition of DAA).

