9.5.3 Objective Outcomes

Shoulder range of motion (ROM) in forward flexion, external and internal rotation will be summarized by group at 26 weeks and one year, along with the changes from Pre-op/Baseline to each time point.

Post-operative cuff integrity is determined through MRI and is classified into five categories, as described by Sugaya et al.¹⁰ type I, sufficient thickness with homogeneously low intensity; type II, sufficient thickness with partial high intensity; type III, insufficient thickness without discontinuity; type IV, presence of a minor discontinuity; type V, presence of a major discontinuity. Data will be summarized by group using frequency distributions.

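### Does the primary healing test fail because the plan does not say which Sugaya types count as healed?

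*Combined protocol and SAP*

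**What the plan says.** The Protocol Summary states "The primary outcome measure is healing evaluation in MRI", and Section 3.4 names the tools as "MRI Post-Operative Assessment (Goutallier Stage and Sugaya Classification").

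Section 3.6 says "Post-operative cuff integrity will be classified utilizing the 5 categories" and lists them. Sections 6.2 and 9.5.3 repeat the list. The two middle types read "type III, insufficient thickness without discontinuity; type IV, presence of a minor discontinuity".

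Section 9.1 plans on one proportion per arm: "The healing rate on the postoperative MRI in the treatment group was assumed to be 75%, and in the control group, 40"%. It uses a one-sided alpha of 0.025 and 90% power, needs 40 per group, and enrols 60 per group to allow for 33% dropout.

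Section 9.5.1 begins "The primary outcome of difference in healing rates between groups will be assessed under the following hypothesis" and tests the six-month rates by chi-square, with success at one-sided p<0.025. For the five Sugaya types, Section 9.5.3 says "Data will be summarized by group using frequency distributions".

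The schedule in Section 6 has a row for "Rotator Cuff Assessment and Healing Index" at baseline and 26 weeks. Section 6.4 gives only the bone-thickness part of that index.

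**The concern.** A chi-square test on healing rates needs one yes/no value per patient, and the plan gives a five-type scale plus a second staging system with no rule for reducing them. Type III fails on thickness but passes on continuity, so both I–II and I–III fit the words. Goutallier stage has no threshold, no rule for combining it with Sugaya and no analysis in Section 9.5. The 75% and 40% rates are tied to neither cut. The Healing Index is scheduled at the same visit with no stated link to healing, and nothing says how readers treat a 1 mm graft that is present in one arm only.

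This is the only test with a success criterion. If the cut were chosen after results by arm were known, the one-sided 0.025 error would not hold. Power could also differ from the stated 90% if the planning rates belong to the other definition.

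**Working it through.** **Inputs.** Rates 0.75 and 0.40, one-sided alpha 0.025, power 0.90, 33% dropout (Section 9.1). The test is the one-sided form of the uncorrected chi-square (Section 9.5.1). No Sugaya distribution is given, so every split below is an assumption.

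**1. The plan's own figure.** With pooled variance and p̄ = (0.75 + 0.40)/2 = 0.575:

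n = [1.960·√(2·0.575·0.425) + 1.282·√(0.75·0.25 + 0.40·0.60)]² / 0.35² = (1.370 + 0.838)² / 0.1225 = 39.8, so 40 per group.

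40/(1 − 0.33) = 59.7, so 60 per group and 120 in all. Both stated figures reproduce. Exact power for 75% v 40% is 90.7% at 40 per arm and 98.0% at 60.

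**2. Error with one cut fixed in advance.** Reject when z = (p_T − p_C)/√(p̄(1 − p̄)·2/n) > 1.960, and sum the binomial probabilities of the rejecting outcomes when both arms share one rate. At 40 per arm:

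- rate 30% or 70%: 2.42%
- rate 40% or 60%: 2.61%
- rate 50%: 2.83%

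The error stays close to 2.5% wherever the cut falls in this range.

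**3. Error if either cut may be claimed.** Nine null splits of I–II / III / IV–V were simulated with 1,000,000 draws each. The chance that at least one cut is significant is 3.9–4.8% at 40 per arm and 4.0–4.7% at 60. The lowest value at 40 per arm is 3.94% (30/10/60) and the highest is 4.84% (20/40/40).

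**4. If the planning rates belong to one cut and the analysis uses the other.** Power is exact; the disagreement share is simulated.

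| Cut with 75% v 40% | Type III, DAA v control | Rates at other cut | Power of other cut, 40 / 60 per arm | Cuts disagree on significance, 40 / 60 |
|---|---|---|---|---|
| I–II | 10% v 10% | 85% v 50% | 93% / 99% | 7.9% / 2.0% |
| I–II | 15% v 15% | 90% v 55% | 96% / >99% | 8.8% / 2.1% |
| I–II | 10% v 20% | 85% v 60% | 72% / 89% | 22.0% / 10.5% |
| I–III | 10% v 10% | 65% v 30% | 90% / 98% | 8.4% / 2.4% |
| I–III | 10% v 20% | 65% v 20% | 99% / >99% | 8.7% / 2.0% |
| I–III | 20% v 10% | 55% v 30% | 64% / 81% | 28.5% / 17.9% |

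In four of the six cases power at the other cut is at least 90% at 40 per arm. The two low cases are those where the arms differ in type III so that the difference shrinks from 35 to 25 points.

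**5. What the text supports.** Sugaya is the only scale whose categories the plan spells out, and it is the one attached to postoperative cuff integrity, so an analyst would build healing from it. Section 2.1 frames failure as retear and as tendon pulling through suture, and only types IV and V involve a discontinuity. That leans towards I–III as healed, without settling it. The Healing Index is not a rival definition: the first bibliography entry presents it as a predictor of healing.

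**The case for a change.** The strongest case is that a primary endpoint should be fully determined by the protocol. Here it is not. Case report forms and their guidelines might hold a definition, but the Supplemental Materials page says they can be changed without an amendment. Section 9 allows interim analyses on regulatory request, and the text available does not say who reads the scans or whether readers know the arm. So nothing written prevents a late choice of cut, and the cost of writing one line is trivial.

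Much of this stands as a description. The cut is missing, Goutallier's role is unstated, and naming both would be good practice. What does not follow is that the planned test is wrong. The 3.9–4.8% error needs a sponsor who picks the winning cut after seeing results, and no section permits that. The low-power cases rest on invented splits. The remedy would leave the choice of cut to the sponsor, which concedes that either is acceptable once fixed.

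The graft point is weaker still. Sugaya types depend on signal and continuity as well as thickness, so counting graft as tendon could move a patient either way. Section 2.1 also mentions neotendon formation, and no section shows that graft and native tendon can be told apart at 26 weeks.

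**Conclusion.** No change follows. This is missing detail that an analyst fills sensibly, most naturally with one cut on the Sugaya scale and Goutallier stage summarised separately. With the cut fixed before results by arm are seen, the one-sided error is 2.4–2.8% at 40 per arm for healing rates of 30–70%, and no stated rule or number is shown to be in error. The tabulation of all five types by group exposes the choice, because both cuts can be rebuilt from it.

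The conclusion rests on one assumption: the cut is set without sight of outcomes by arm. If it were not, the error could reach 3.9–4.8% at 40 per arm under the assumed splits. How far power departs from 90% cannot be estimated from the documents; the assumed cases run from 64% to 99% at 40 per arm, and from 81% to over 99% if all 60 per arm are evaluable.

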3.5 Subjective Outcome Measures

The subjective data will be collected as listed in the table: The American Shoulder and Elbow Surgeons Shoulder Score, (ASES score), Veterans RAND Health Survey (VR-12), Single Assessment Numerical Evaluation (SANE), and the Visual Analogue Scale (VAS pain) surveys.

3.6 Objective Outcome Measures

Shoulder range of motion (ROM) in forward flexion, external rotation at the side, external rotation at 90° of abduction, and internal rotation at 90° of abduction will be measured with a goniometer. Internal rotation will also be estimated to the nearest spinal level. The lead investigator or assigned research staff at each site will perform all measurements.

The MRI imaging will be collected according to standard of care pre-operatively and then at the 26 ± 8 weeks timepoint.

A standard shoulder MRI protocol utilizing a minimum of a 1.5 Tesla magnet shall be utilized. A recommendation for setting is: 5 pulse sequences, sagittal oblique T1-weighted and fast spin echo (FSE) T2-weighted with fat saturation, axial FSE proton density and FSE T2-weighted with fat saturation, and coronal oblique FSE T2-weighted with fat saturation. Post-operative cuff integrity will be classified utilizing the 5 categories described by Sugaya et al¹⁰: type I, sufficient thickness with homogenously low intensity; type II, sufficient thickness with partial high intensity; type III, insufficient thickness without discontinuity; type IV, presence of a minor discontinuity; type V, presence of a major discontinuity.

4 STUDY ENROLLMENT AND WITHDRAWAL

4.1 Study Population and Study Duration

This study population will include both male and female patients, with an anticipated enrollment goal of 120 subjects (n= 60 subjects per group) study-wide from the practices of all participating sites.

Subjects will be recruited from the surgeon's patient population or referrals from other physicians. The enrollment period is estimated to be 12 months. Study subjects' length of participation is 24 months. The total estimated study duration is approximately three years. Subjects will be considered enrolled at the time of treatment.

